Appendix 2 Definition of Acute Idiopathic Pulmonary Fibrosis Exacerbation

Definition and diagnostic criteria are defined as follows [29]:

Definition:

An acute, clinically significant respiratory deterioration characterized by evidence of new widespread alveolar abnormality.

Diagnostic criteria:

- Previous or concurrent diagnosis of IPF
- Acute worsening or development of dyspnea typically < 1 month duration
- Computed tomography with new bilateral ground-glass opacity and/or consolidation superimposed on a background pattern consistent with usual interstitial pneumonia pattern
- Deterioration not fully explained by cardiac failure or fluid overload

[figure not shown]

Figure 3. Proposed conceptual framework for evaluation of acute respiratory deterioration in idiopathic pulmonary fibrosis (IPF). Acute respiratory deterioration of IPF (defined as “typically <1 month in duration”) can be categorized as extraparenchymal (e.g., pulmonary embolism, pneumothorax, pleural effusion) or parenchymal. Parenchymal causes that demonstrate new bilateral ground-glass opacification (GGO)/consolidation on computed tomography (CT) that is not fully explained by cardiac failure or fluid overload are categorized as acute exacerbations of IPF, regardless of the presence or absence of a known trigger (e.g., infection). Acute exacerbations are further categorized as triggered acute exacerbation or idiopathic acute exacerbation, depending on whether an underlying trigger for acute exacerbation is found.

Appendix 3 Contraindications for 6-Minute Walk Test

Absolute contraindications:

- Unstable angina during the previous month [27]
- Myocardial infarction during the previous month [27]
- Oxygen saturation measured by pulse oximetry <88 % after 10 minutes of rest of breathing room air or at baseline oxygen flow rate [30].

Relative contraindications [27]

- Resting heart rate >120 beats per minute
- SBP >180 mmHg
- DBP >100 mmHg

Source: [27]

Appendix 4 Normal Ranges

NORMAL RANGES FOR VITAL SIGNS

Normal ranges applicable in supine position (after 5 minutes):

Systolic blood pressure (mmHg)	Diastolic blood pressure (mmHg)	Heart rate (bpm)	Oral/Tympanic temperature (°C)	Respiratory rate (RR) (breaths/minute)
$90 \leq \text{SBP} \leq 150$	$45 \leq \text{DBP} \leq 90$	$50 \leq \text{HR} \leq 100$	$35.5 \leq t^{\circ} \leq 37.5$	$12 \leq \text{RR} \leq 18$

NORMAL RANGES FOR ECG PARAMETERS

Normal ranges applicable in supine position (after 5 minutes):

PR (ms)	QRS (ms)	QTcF (ms)	Heart rate (bpm)
$120 \leq \text{PR} \leq 220$	$\text{QRS} \leq 120$	QTcF ≤ 450 (male) QTcF ≤ 460 (female)	$50 \leq \text{HR} \leq 100$

Appendix 5 Non-exhaustive List of Known Breast Cancer Resistance Protein Substrates

Substrate liability demonstrated in vitro:

4-methylumbelliferone sulfate
Daunorubicin
Doxorubicin
Estradiol-17beta-glucuronide
Estrone 3-sulfate
Hematoporphyrin
Imatinib
Methotrexate
Mitoxantrone
Pheophorbide A
Pitavastatin
Rosuvastatin
SN-38
SN-38 glucuronide
Sulfasalazine
Topotecan

In vivo substrates, from clinical studies:

Rosuvastatin
Pitavastatin
Topotecan

Appendix 6 Non-exhaustive List of Known Organic Cation Transporter 2 Substrates

Known OCT2 substrates:

Amantadine
Amiloride
Cimetidine
Dopamine
Epinephrine
Famotidine
Histamine
Lamivudine
Memantine
Metformin*
N-methylpyridinium
Norepinephrine
Prostaglandin E2
Prostaglandin F2alpha
Ranitidine
Serotonin
Tetraethylammonium
Varenicline*

* denotes drugs that can potentially be used for in vivo (clinical) studies of the designated transporter

Appendix 7 Exposure to Radiation

HRCT for IPF diagnosis

A chest scan for IPF diagnosis will expose a subject to approximately 4–5 mSv.

[REDACTED]

[REDACTED]

A radiation dose of approximately 2–2.5 mSv is equivalent to approximately 1 year of background radiation (based on the assumption of an average "effective dose" from natural background radiation is of 3.1 mSv per year in the US and 2.4 mSv per year in Europe [31, 32]).

Appendix 8 Non-exhaustive List of Medications Known to be Dual Inhibitors of CYP3A4 and CYP2C19 Enzymes

Medications known to be dual inhibitors of CYP3A4 and CYP2C19 are prohibited during the study. The following is a non-exhaustive list of these medications as guidance for the investigator.

- Chloramphenicol
- Cimetidine
- Fluvoxamine
- Ketoconazole
- Voriconazole

Appendix 9 Non-exhaustive List of Medications Known to be Strong Inducers of CYP3A4 or CYP2C19

Medications known to be strong inducers of CYP3A4 or CYP2C19 are prohibited during the study. The following is a non-exhaustive list of these medications as guidance for the investigator.

- Barbiturates
- Carbamazepine
- Modafinil
- Oxcarbazepine
- Phenobarbital
- Phenytoin
- Pioglitazone
- Rifabutin
- Rifampin
- St. John's Wort
- Norethindrone

IDMC	Independent Data Monitoring Committee
IMP	investigational medicinal product
INF	infinity
IPF	idiopathic pulmonary fibrosis
IWRS	interactive web response system
LB	lung biopsy
LLN	lower limit of normal
LS	least squares
MAR	missing-at-random
MNAR	missing not at random
OC	observed cases
█	█
PFT	pulmonary function test
PK	pharmacokinetic(s)
PP	per protocol
q.d.	once daily (quaque die)
QTcF	QT interval corrected for the heart rate using Fridericia's formula
SAE	serious adverse event
SAP	statistical analysis plan
SE	standard error
SGRQ	St. George's Respiratory Questionnaire
SOC	standard of care
TEAE	treatment-emergent adverse event
█	█
ULN	upper limit of the normal range
US	United States
USM	urgent safety measure

1. INTRODUCTION

This statistical analysis plan (SAP) describes the final and potential interim statistical analyses of study GLPG1205-CL-220 (PINTA). An interim analysis may be performed upon sponsor decision to allow planning of future clinical studies. In addition, an unblinded review of data will be performed on a regular basis by an Independent Data Monitoring Committee (IDMC). The IDMC analyses are detailed in a separate SAP and will be provided to the IDMC by an independent, unblinded statistical support group.

A separate pharmacometric analysis plan will be written for the population pharmacokinetics (PK) [REDACTED] analyses.

Technical details on derivations and mock tables, listings and figures (TLFs) will be presented in a separate document.

The statistical analysis will process and present the results following the International Council for Harmonization (ICH) standards, particularly the ICH-E3, ICH-E6, ICH-E9, ICH-R9 (R1) and ICH-E14 guidelines.

2. STUDY DESIGN AND OBJECTIVES

2.1. Study Objectives

2.1.1. Primary Objective

- To evaluate the efficacy of GLPG1205 treatment in subjects with idiopathic pulmonary fibrosis (IPF) on pulmonary function as evaluated by forced vital capacity (FVC) compared to placebo over 26 weeks.

2.1.2. Secondary Objectives

- To evaluate the safety and tolerability of GLPG1205 treatment compared to placebo over 26 weeks.
- To evaluate the impact of GLPG1205 treatment compared to placebo on time to any major events (whichever occurs first) defined as:
 - Mortality (all-cause and respiratory-related)
 - Hospitalization (all-cause and respiratory-related)
- To evaluate the changes from baseline in functional exercise capacity measured by the 6-minute walk test (6MWT), in IPF subjects treated with GLPG1205 compared to placebo at Week 26.
- To evaluate the changes in quality of life measures in IPF subjects treated with GLPG1205 compared to placebo over 26 weeks.
- To evaluate the PK of GLPG1205, nintedanib and pirfenidone in IPF subjects.

2.1.3. Other Objectives

2.2. Study Endpoints

2.2.1. Primary Endpoint

- Change from baseline in FVC (mL) over 26 weeks compared to placebo.

2.2.2. Secondary Endpoints

- Safety and tolerability changes over time (baseline to 26 weeks).
- Time to any of major events (whichever occurs first) defined as:
 - Death (all-cause and respiratory-related)
 - First hospitalization (all-cause and respiratory-related)
- Change from baseline 26 weeks in functional exercise capacity, assessed by the 6MWT at Week 26.
- Change from baseline until 26 weeks in quality of life measures, assessed by the St. George's Respiratory Questionnaire (SGRQ) total score and domains and proportion of SGRQ responders.
- Plasma concentrations of GLPG1205, nintedanib and pirfenidone.

2.2.3. Other Endpoints

2.2.4. Adjudication

The following endpoints will be adjudicated by the clinical endpoint adjudication committee (CEAC):

- Mortality: all-cause and respiratory-related (2 separate endpoints)
- Hospitalization: all-cause and respiratory-related (2 separate endpoints)

Adjudicated endpoints will be used in the time-to-event analyses described in Section 5.2.3.1 and not the corresponding investigator-reported events. Consistency with the investigator-reported information will be investigated.

2.3. Study Design

This study is a randomized, double-blind, parallel group, placebo-controlled, multicenter, Phase 2 study.

Approximately 60 eligible subjects with a centrally confirmed IPF diagnosis are planned to be randomized in a 2:1 ratio to GLPG1205 100 mg q.d. taken as 2 capsules, or matching placebo once daily (q.d.) administered for 26 weeks on top of local standard of care (SOC). Standard of care is defined as receiving nintedanib, pirfenidone, or neither nintedanib nor pirfenidone.

Individual dose reductions of GLPG1205 will be allowed once in case of intolerance or toxicity at the discretion of the investigator. Subjects may have their dose of investigational medicinal product (IMP) reduced from 100 mg (2 capsules) q.d. to 50 mg (1 capsule) q.d. for the remainder of the study. Should the intolerance or toxicity continue, IMP may be discontinued, and the subject may be withdrawn from the study.

[figure not shown]
During the course of the study (post randomization) further adaptations of the treatment with nintedanib or pirfenidone due to e.g. intolerance or initiation of either nintedanib or pirfenidone is allowed based on the medical needs of the individual as judged by the investigator.

Enrolled subjects will come to the clinical study center at screening, Day 1 (baseline), Week 2, Week 4, Week 8, Week 12, Week 16, Week 20, Week 26, and, if applicable (i.e. for early IMP discontinuation), the end of treatment visit (EOT). In addition, a follow-up visit will be planned 4 weeks after the last administration of IMP (i.e. Week 30/EoS). The end of the study is reached when the last follow-up visit as planned according the Schedule of Activities (Section 2.5) of the last subject is performed.

Subjects who stop IMP early need to be encouraged to complete the EOT and follow-up visit for safety assessments and pulmonary function, but will not be obliged to do so.

To enhance the safety of the subjects and integrity of the study data, an IDMC will be implemented and clinical endpoint adjudication will be performed. Details are stipulated in the study protocol and the respective charters.

A schematic diagram of the clinical study design is provided below.

The subjects will be in the study for a duration of approximately 34 weeks: up to 4 weeks of screening, 26 weeks of treatment, and 4 weeks of follow-up.

2.4. Clinical Study Protocol (CSP) and CSP Amendments

This SAP is based on the protocol version 3.0 (amendment 2), dated 30-Apr-2020.

2.5. Schedule of Assessments

For detailed instructions on the clinical study procedures, please see Section 6.1 of the protocol.

EVENT	SCR	TREATMENT PERIOD									FU
Study visit	¹	²	3	4	5	6	7	8	9	EOT	10/ EOS
Study week (W) or day (D) ± days (d)	D-28 to D-1	D1	W2 ±2d	W4 ±2d	W8 ±4d	W12 ±4d	W16 ±4d	W20 ±4d	W26 ⁶ ±6d		W30 ⁷ ±4d
Informed consent	✓										
Dispense subject participation card	✓										
Send HRCT (historical or new ²) for central review	✓										
Send LB (if available) for central review	✓										
Demographics	✓										
Medical history/concurrent illnesses	✓										
Alcohol consumption and smoking habits	✓										
Inclusion/exclusion criteria	✓	✓									
Physical examination	✓ ³	✓	✓	✓		✓		✓	✓ ³	✓ ³	✓ ³
12-Lead ECG	✓	✓	✓			✓		✓	✓	✓	✓
Vital signs	✓	✓	✓	✓	✓	✓	✓	✓	✓	✓	✓

¹ Screening assessments need to be performed within 28 days before Day 1 and may be split into multiple days or visits.

² If there is no historical HRCT available, a new HRCT needs to be planned and performed. Only if for logistic reasons it is not possible to perform a new HRCT within the planned screening period and after approval of the medical monitor it is allowed to extend the screening period with maximum 2 weeks.

³ At screening include height and weight; at Visit 9/EOT and Visit 10/EOS include weight.

EVENT	SCR	TREATMENT PERIOD									FU
		²	3	4	5	6	7	8	9	EOT	
Study visit	¹¹										
Study week (W) or day (D) ± days (d)	D-28 to D-1	D1	W2 ±2d	W4 ±2d	W8 ±4d	W12 ±4d	W16 ±4d	W20 ±4d	W26 ⁶ ±6d		W30 ⁷ ±4d
Spirometry	✓ ⁴	✓ ⁴		✓	✓	✓	✓	✓	✓ ⁴	✓	✓
SGRQ		✓				✓			✓	✓	
Clinical laboratory tests (hematology, coagulation, clinical chemistry, urinalysis)	✓	✓	✓	✓	✓	✓	✓	✓	✓	✓	✓
Serology	✓										
FSH test	✓										
Pregnancy test	✓										
PK blood samples		✓		✓		✓		✓	✓		✓
DLCO	✓ ⁵										
6MWT	✓	✓							✓	✓	

⁴ Spirometry can be repeated once if acceptability and repeatability criteria as specified by ATS/ERS/JRS/ALAT are not met after confirmation by central reader.

⁵ [REDACTED]

⁶ In case Visit 9 cannot be performed on site within the visit window due to the COVID-19 pandemic, the study medication intake and the corresponding time window for Visit 9 can be extended up to +56 days or shortened up to -28 days.

⁷ In case Visit 10 cannot be performed on site within the visit window due to the COVID-19 pandemic, the corresponding time window for Visit 10 can be extended up to +28 days or shortened up to -7 days.

EVENT	SCR	TREATMENT PERIOD									FU	
		1	2	3	4	5	6	7	8	9		EOT
Study week (W) or day (D) ± days (d)	D-28 to D-1	D1	W2 ±2d	W4 ±2d	W8 ±4d	W12 ±4d	W16 ±4d	W20 ±4d	W26 ⁶ ±6d			W30 ⁷ ±4d
Randomization		✓										
Dispense subject diary		✓	✓	✓	✓	✓	✓	✓	✓			
Collect subject diary			✓	✓	✓	✓	✓	✓	✓	✓	✓	
Dispense IMP		✓	✓	✓	✓	✓	✓	✓	✓			
Collect returned IMP and review IMP compliance			✓	✓	✓	✓	✓	✓	✓	✓	✓	
Dose IMP		daily throughout the treatment period										
Concomitant medication		throughout the study										
AE assessment		throughout the study										

6MWT=6-Minute Walk Test; AE=adverse event; D=Day; d=days; DLCO=diffusing capacity for the lungs for carbon monoxide; ECG=electrocardiogram; EOS=end of study; EOT=end of treatment visit; ██████████ FSH=follicle stimulating hormone; FU=follow-up; HRCT=high-resolution computed tomography; IMP=investigational medicinal product; ██████████ PK=pharmacokinetic; SAE=serious adverse event; SCR=screening; SGRQ=St George's Respiratory Questionnaire; LB= lung biopsy; W=Week

2.6. Sample Size Justification

See Section 7.1 of the CSP.

2.7. Randomization and Blinding

See Section 4.4 of the CSP.

It is acknowledged that the sponsor may be unblinded by a potential interim analysis. However, all efforts will be made to restrict the access to the study results so that personnel involved with the study conduct remain blinded, at least at an individual subject level.

3. GENERAL METHODOLOGY

3.1. Analysis Sets

The analysis set will always be indicated in a subtitle in the table, listing, or figure.

3.1.1. All Screened Analysis Set

All subjects who signed an informed consent form (ICF) to participate in this study.

3.1.2. All Randomized Analysis Set

All screened subjects who were randomized in this study.

3.1.3. Full Analysis Set

All randomized subjects who have used at least 1 dose of IMP.

3.1.4. Per-Protocol Analysis Set

Subpopulation of the Full Analysis Set (FAS), excluding all subjects/data points with major protocol deviations impacting the efficacy results (determined during the blinded data review meeting). These protocol deviations are determined prior to unblinding and database lock and are entered in the database.

The Per-Protocol analysis is only planned if at least 10% of the subjects are omitted from the Per-Protocol Analysis Set.

If a subject is unblinded (e.g. in case of a serious adverse event [SAE]), all their efficacy data will be disqualified from the Per-Protocol Analysis Set.

3.1.5. Pharmacokinetic Analysis Set

Subset of the FAS, selecting all subjects who have available and evaluable PK plasma concentration data (e.g. excluding all protocol deviations or AEs that may have an impact on the PK analysis).

[REDACTED]

[REDACTED]

3.2. Randomized Versus Actual Treatment Group

For subject information, efficacy, safety, [REDACTED] parameters, the treatment group as assigned by the randomization will be used in the analysis (i.e. as-randomized analysis).

For PK, the actual treatment will be used in the analysis.

Differences between the randomized and actual treatment group will be listed.

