7.1. DETERMINATION OF SAMPLE SIZE

The aim of this proof-of-concept study is to show a trend in treatment difference for the primary endpoint (change from baseline in FVC over 26 weeks), therefore no formal sample size calculation was performed. In the following paragraph, the variability of the estimated treatment difference for the proposed sample size of 60 subjects is illustrated.

Consider 40 and 20 evaluable subjects in the GLPG1205 and placebo arm, respectively, and an aim of a 50:50 balanced study population being either on nintedanib/pirfenidone or neither. Further, assume for FVC change from baseline at Week 26 a common standard deviation of 200 mL, a true treatment difference of 50 mL in the population receiving nintedanib or pirfenidone and a true treatment difference of 80 mL in the population receiving neither nintedanib nor pirfenidone. Under these assumptions and taking into account 10% dropout, the probability to observe a treatment effect of more than 40 mL in the total study population is 67% and the probability to observe a treatment effect of more than 20 mL is 78%.

Approximately 60 subjects are planned to be randomized into the study.

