7.3.5. Analyses of Safety Data

All safety analyses will be performed using the full analysis set (Section 7.2.3). All safety data collected on or after the first dose of IMP administration up to the last follow-up visit after the last dose of IMP, unless specified otherwise, will be displayed in listings of individual data and/or summarized by treatment group according to the IMP received. Clinical safety will be addressed by assessing AEs, laboratory assessments, physical examinations, vital signs, and 12-lead ECGs.

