5.1.7.2. Presentation of Results

Summary statistics per treatment group and overall will be provided for each compliance and extent of exposure parameter. Frequency tables will be provided for the compliance parameters, using the following categories: <80%; $80\% \leq x < 100\%$; 100%; $100\% < x \leq 120\%$; > 120%.

A listing will be provided of the subjects who took incorrect study medication (GLPG1205 instead of placebo, or vice versa) for at least part of the treatment period, all GLPG1205/placebo records are to be included to provide an overview of the amount of cross-treatment relative to the total treatment period.

In addition, a listing of the subjects who had their study medication down-titrated or interrupted for at least part of the treatment period will be provided. All GLPG1205/placebo records are to be included to provide an overview of the amount of down-titration/interruption relative to the total treatment period.

Finally, a listing of the subjects receiving investigational product from specific batches, where more than one batch was used (showing the batch numbers of the investigational products actually used, including the expiration dates) will also be provided.

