5.3. Safety Analyses

Safety analyses will be performed on the FAS.

Safety tables will be presented by treatment group.

Safety parameters will be analyzed descriptively (see Section 3.5.2 and Section 3.5.3). No formal testing will be performed to compare the treatment groups.

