5.3.1.7. Presentation of Results

The analysis will focus on AEs reported during the treatment period. AEs reported during the screening or follow-up period will only be listed.

All adverse events tables will show the number of subjects with TEAEs.

A summary table will be provided, showing the number (percent) of subjects with at least one:

- TEAE
- serious TEAE
- TEAE leading to death
- TEAEs by worst severity
- TEAE that was considered related to GLPG1205/placebo
- TEAE that was considered related to pirfenidone
- TEAE that was considered related to nintedanib
- TEAE for which GLPG1205/placebo was reduced
- TEAE for which GLPG1205/placebo was temporarily stopped
- TEAE for which GLPG1205/placebo was permanently stopped
- TEAE for which pirfenidone was reduced
- TEAE for which pirfenidone was temporarily stopped
- TEAE for which pirfenidone was permanently stopped
- TEAE for which nintedanib was reduced
- TEAE for which nintedanib was temporarily stopped
- TEAE for which nintedanib was permanently stopped

For each line, the difference in percentage of subject with an AE between placebo and GLPG1205 will be included, together with the 95% CI of the difference using the method of Miettinen and Nurminen.

Frequency tabulations, by system organ class and preferred term, of the number (percent) of subjects with a TEAE will be presented. Similar tables will be provided (by worst severity) for TEAEs of grade 3/4, TEAEs related to GLPG1205/placebo and for TEAEs related to SOC.

Serious adverse events (including AEs leading to hospitalization), AEs leading to death, leading to respiratory-related hospitalization (as reported by the investigator), of grade 3/4, leading to discontinuation of GLPG1205/placebo, leading to a temporary stop or dose reduction of GLPG1205/placebo, leading to a permanent stop, temporary stop, or dose reduction of SOC, pre- and post-treatment adverse events will be listed.

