5.5. Changes to the Planned Analyses, Not Covered by Protocol Amendments

[REDACTED]

Data after lung transplant will be excluded from all efficacy analyses.

[REDACTED]

In addition to descriptive statistics, ANCOVA models were included for the analysis of 6MWT distance, SGRQ score [REDACTED]

If changes are needed after unblinding these will be documented in the CSR with an explanation for the reason for the change.

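### SAP 3.2 tabulates safety by randomised arm, while protocol 7.3.5 tabulates it by IMP received; the tables differ if any subject takes the other arm's IMP.

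*SAP*

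**What the plan says.** Protocol 7.3.5 states that safety data from first dose to last follow-up visit, "unless specified otherwise, will be displayed in listings of individual data and/or summarized by treatment group according to the IMP received".

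SAP 3.2 is a short section devoted to randomised versus actual treatment. It reads "For subject information, efficacy, safety, [REDACTED] parameters, the treatment group as assigned by the randomization will be used in the analysis" and labels this an as-randomised analysis. It uses actual treatment for PK and lists differences between randomised and actual group.

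SAP 2.4 fixes the version: "This SAP is based on the protocol version 3.0 (amendment 2), dated 30-Apr-2020". SAP 5.3 runs safety on the full analysis set, by treatment group, and does not override 3.2. It adds "No formal testing will be performed to compare the treatment groups". SAP 5.3.1.7 nevertheless gives a comparative estimate for every line of the AE summary: "the difference in percentage of subject with an AE between placebo and GLPG1205 will be included", with a Miettinen-Nurminen 95% interval.

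The SAP foresees wrong-arm intake. SAP 5.1.7.2 lists subjects who took the wrong study medication, where "all GLPG1205/placebo records are to be included to provide an overview of the amount of cross-treatment relative to the total treatment period". SAP 5.1.3 lists planned and actual group with discrepancies flagged.

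**The concern.** The two governing documents prescribe different tables for the same data as soon as one subject takes the other arm's IMP. For a subject wholly on the other product, the SAP table places that subject's events under a treatment never taken. For a subject mainly on the other product, it places them under the treatment taken for the smaller part of the period. This affects the AE tables and risk differences, and also the laboratory, ECG and vital-sign tables by treatment group.

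Safety and tolerability against placebo is the first secondary objective, and the placebo arm is planned at about 20 subjects, so one subject is 5 percentage points of that arm. Misallocation on average shrinks a true drug effect, which is the unhelpful direction for safety. If the rule is settled only after a misdosed subject with a serious event is known, the choice is open to the charge of being data-driven.

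**Working it through.** **Plan's own figure.** The plan gives no figure on this point. Its only design figures, in protocol 7.1, are 67% and 78% for an observed FVC effect above 40 and 20 mL. They reproduce: mean difference (50 + 80)/2 = 65 mL; with 10% dropout, 36 and 18 subjects; SE = 200 × √(1/36 + 1/18) = 57.74; probabilities Φ(25/57.74) = 0.6675 and Φ(45/57.74) = 0.7821. Nothing below depends on them.

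**The texts side by side.**

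| Question | Protocol 7.3.5 | SAP 3.2 |
|---|---|---|
| Arm used for safety | IMP received | Randomised arm |
| Actual treatment used for | Safety | PK only |
| Partly crossed-over subject | Not defined | Defined: randomised arm |

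The full analysis set decides who is included, not under which arm, so it does not settle the matter.

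**Inputs for the size.** Arm sizes come from protocol 7.1: "Consider 40 and 20 evaluable subjects in the GLPG1205 and placebo arm, respectively". The rest is assumed because the documents give no misdosing or event rate: equal event rates as randomised (difference 0.0), and one subject wholly on the other arm's IMP who is moved to the arm received.

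**Formula.** Risk difference = GLPG1205 rate minus placebo rate, in points. There are four possible cases:

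- A: placebo subject with the event took GLPG1205
- B: placebo subject without the event took GLPG1205
- C: GLPG1205 subject with the event took placebo
- D: GLPG1205 subject without the event took placebo

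Example at 5%: as randomised, 2/40 − 1/20 = 0.0. As treated: A, 3/41 − 0/19 = +7.3; B, 2/41 − 1/19 = −0.4; C, 1/39 − 2/21 = −7.0; D, 2/39 − 1/21 = +0.4.

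| Event rate | As-randomised 95% CI (width) | A | B | C | D | Largest shift / width |
|---|---|---|---|---|---|---|
| 5% | −19.4 to 12.7 (32.1) | +7.3 | −0.4 | −7.0 | +0.4 | 23% |
| 10% | −21.5 to 15.5 (37.0) | +6.9 | −0.8 | −6.6 | +0.7 | 19% |
| 25% | −25.1 to 21.4 (46.5) | +5.8 | −1.9 | −5.5 | +1.8 | 12% |
| 50% | −25.9 to 25.9 (51.8) | +3.9 | −3.9 | −3.7 | +3.7 | 8% |
| 80% | −19.8 to 24.3 (44.1) | +1.5 | −6.2 | −1.5 | +5.9 | 14% |

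Every shifted estimate lies inside the as-randomised interval.

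**Average shift.** Weight the cases by the chance that the misdosed subject had the event. For a placebo subject this is rate × |A| + (1 − rate) × |B|. At 5%: 0.05 × 7.3 + 0.95 × 0.4 ≈ 0.7. For either direction of misdosing, the averages are about 0.7 (5%), 1.3 to 1.4 (10%), 2.8 to 2.9 (25%), 3.7 to 3.9 (50%) and 2.3 to 2.5 (80%).

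**Expected dilution of a true difference.** With assumed true rates of 20% and 10%:

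- One misdosed placebo subject: 20 − (19 × 10 + 20)/20 = 9.5 of 10 points, a loss of 1/20 = 5%.
- One misdosed GLPG1205 subject: (39 × 20 + 10)/40 − 10 = 9.75 of 10 points, a loss of 1/40 = 2.5%.

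**The case against.** The protocol delegates statistical methods to a SAP finalised before unblinding, and SAP 3.2 is explicit and complete: even a partly crossed-over subject has a defined arm. Three sets of listings (SAP 3.2, 5.1.3 and 5.1.7.2) would let a reader of a study of about 60 subjects find any affected subject. Neither document reports misdosing. Safety is descriptive, so no test, alpha or power is touched. All of this stands and limits the weight of the point. It does not reconcile the texts, and a listing does not correct a table or a risk difference.

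The clause in protocol 7.3.5 allowing exceptions might be read as licence for the SAP rule. It follows the wording on the collection period and most naturally qualifies that. Even on the wider reading, the readable SAP gives no reason for regrouping.

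A reader might infer three stronger things that the documents do not support:

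- That the SAP departs from the protocol without declaring it. SAP 5.5 is where departures are recorded. Its readable entries, such as "Data after lung transplant will be excluded from all efficacy analyses", do not mention safety grouping, but part of the section is blacked out, so an entry cannot be excluded.
- That any misdosed subject is tabulated under a treatment not taken. This is exact only for a subject wholly on the other product; one mainly on it did take some assigned IMP.
- That one such subject typically moves a risk difference by 4 to 7 points, or always hides harm. Those figures are the largest of four cases at each assumed rate, and in a single case the as-randomised difference can err in either direction. Only the expectation is towards dilution.

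**Conclusion.** The conflict is real in the current texts and should be resolved, at modest weight. Followed as written, the SAP would count a wholly misdosed subject's safety data under a treatment not taken, contrary to the protocol. If nobody is misdosed, the tables are identical and only the wording needs repair. Under the stated assumptions, one wholly misdosed subject shifts a risk difference by at most about 4 to 7 points depending on the event rate, by as little as 0.4, and by about 0.7 to 4 on average. The shift stays within an as-randomised interval 32 to 52 points wide. Expected dilution of a true difference is 5% for one placebo subject or 2.5% for one GLPG1205 subject. The consequence is a shifted estimate and interval, not a changed test. The textual conflict rests on no assumption; the sizes rest on the assumed event rates and a single misdosed subject.

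**What to change.** Before unblinding, amend SAP 3.2 so that subject information and efficacy stay as randomised and safety is tabulated by IMP actually received, as in protocol 7.3.5. Add one sentence assigning partly crossed-over subjects to an arm, for example the IMP taken for most of the treatment period, and point to the listings already planned in SAP 3.2, 5.1.3 and 5.1.7.2.

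If the sponsor prefers as-randomised safety, the alternative is to state and justify that departure in SAP 5.5 and add a supportive as-treated AE table.

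The cost is one or two sentences. Actual treatment is already needed for PK, but the readable SAP does not define it for mixed exposure, so that definition has to be written. A small downside remains: any single-arm rule still misplaces some AEs of partly crossed-over subjects, and the 5.1.7.2 listing is where a reader can see them.
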